##### **Aim 2: Conduct a pilot randomized controlled trial to assess the feasibility, acceptability and preliminary impact of the *LinkPositively* intervention for Black WLHA affected by interpersonal violence, in preparation for a large-scale R01.**

Eighty Black WLHA ever experiencing interpersonal violence will be randomly assigned (1:1) to receive *LinkPositively* or standard of care Ryan White services, with self-reported, biological, and clinical outcomes collected at baseline, 3- and 6-month follow-up visits. Intervention use data will be collected throughout the intervention period to examine feasibility, acceptability, and the associations between components used and study outcomes. Primary outcomes are retention in HIV care, ART adherence, and viral suppression, whereas socio-structural mechanism of change variables are social support and

activation of social support networks, self-efficacy, and utilization of ancillary support services. To minimize recall bias and/or social desirability bias, that may occur with the use of audio computer-assisted self-interviews, we will use objective data to measure the main outcomes. Retention in HIV care and viral suppression will be based on medical record data and ART adherence will be measured using hair samples assayed for tenofovir and emtricitabine. The proposed study will benefit the advancement of HIV prevention science by harnessing mobile technology to promote retention in HIV care and ART adherence among US Black WLHA affected by interpersonal violence and co-occurring adverse mental health and substance abuse – an underserved, marginalized population. If the LinkPositively intervention is efficacious through an eventual R01 mechanism, it will change the paradigm for addressing the unique HIV treatment needs for Black women dually affected by HIV and interpersonal violence.

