**Quantitative Survey.** The quantitative survey will include the following sections: (1) Demographic questions (e.g. age, biological sex at birth, gender identity, race/ethnicity, education, sexual orientation, marital status, employment, number of children, housing status, medical insurance status, food insecurity); (2) Socioeconomic status; (3) Mental health and behavioral health history (e.g. depression, anxiety, alcohol and substance use diagnosis and/or abstinence, lifetime history of trauma); (4) HIV care and treatment history (e.g. obtaining medical care, usual source of medical care, treatments, medications, insurance status, barriers to HIV treatment, self-reported adherence, adherence self-efficacy); (5) Support and Coping (e.g. social support, coping self-efficacy, ancillary support utilization); (6) Health care interactions (e.g. HIV stigma, medical mistrust) (7) Syndemic factors (e.g. interpersonal violence). [See Quantitative Survey].

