### **Medical Record Chart Abstraction**

During the passive follow-up period (7-12 months post-baseline), the research team will utilize the signed Release of Information (ROI) forms and HIPAA Authorization Forms of all study participants (participant consent collected at Baseline Study Visit), in order to request medical chart data for all participants from local HIV care providers to obtain data on clinic visits, HIV viral load, and CD4 values. Data will be entered into the REDCap Electronic Data Capturing System. These medical chart data extractions will be conducted periodically, given the staggered enrollment period.

To safeguard confidentiality, for the quantitative data collection, each participant will receive a unique patient identification number (PID) and names will never be used in conjunction with PID numbers. This unique PID number will appear on the survey, tracking forms (e.g., scrip payment receipt, cell phone tracking form), locator and screening forms. Participant confidentiality will be maintained through use of the unique PID and secure networks where data are stored. All laboratory data will be electronically transferred to the UCSD Data Management Center via password protected electronic files. At the UCSD Data Management Center, all computer files will be identifiable only by the PID number.

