## Statistical Analysis Plan

The statistical plan includes measuring feasibility of delivering the intervention, the acceptability of the LinkPositively intervention, and the impact of the intervention.

**Feasibility** The first step in assessing feasibility of delivering the intervention was by creating a Consort flow diagram tracking screening, eligibility, decision to participate, participation at baseline, and participation at 3-month and 6-month follow-ups. The second step in assessing feasibility was to compute the percentage of participants at baseline who were retained at 3-month follow-up and 6-month follow-up, and comparing proportion trends between the intervention and control groups. We used the following retention cut-off percentages to assess feasibility: a) 90+% = strong feasibility; b) 80-89% = acceptable feasibility; c) 70-79% = modest feasibility with a need for improvement; d) <70% = unacceptable.

**Acceptability** We assessed acceptability of the intervention by asking participants in the LinkPositively group about: 1) the quality rating of the program/app, 2) whether or not they received the type of program/app they were anticipating, 3) to what extent the program/app met their needs, 4) whether or not they would recommend the program/app, 5) level of satisfaction with the help received; 6) whether or not the program helped them deal more effectively with their problems, 7) level of satisfaction with the program received, and 8) whether or not they would seek help from the program/app again.

These measures of acceptability were assessed at both 3-month and 6-month follow-ups. At each timepoint, we computed mean scores and standard deviations, as well as median scores and interquartile ranges, for all continuous variables. We calculated frequency and percentages for all categorical variables.

**Intervention Impact** To estimate the preliminary effect of the intervention on primary outcomes we examined differences by group (intervention vs control) in responses to HIV care outcomes over time, ART adherence over time, and mental health outcomes over time. Responses were collected at baseline, 3-month follow-up, and 6-month follow-up. Due to the small n's, we calculated median scores and interquartile ranges for all continuous variables, and frequency/percentages for categorical variables. These statistics were stratified by group, and trends were compared, but significance could not be calculated due to low power.

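### The SAP's Intervention Impact paragraph aims to estimate an effect but names no between-arm measure or confidence interval, and gives an incorrect reason for omitting significance.

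*Combined protocol and SAP*

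**What the plan says.** The SAP's Intervention Impact paragraph states its purpose as follows: "To estimate the preliminary effect of the intervention on primary outcomes we examined differences by group". The outcomes it lists are HIV care, ART adherence and mental health, at baseline, 3 months and 6 months.

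The statistics are given in one sentence: "Due to the small n's, we calculated median scores and interquartile ranges for all continuous variables, and frequency/percentages for categorical variables". These are stratified by arm, and the paragraph ends by saying that "trends were compared, but significance could not be calculated due to low power".

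Protocol section 6 (Aim 2) gives the context. "Primary outcomes are retention in HIV care, ART adherence, and viral suppression", and the pilot is run "in preparation for a large-scale R01". The same section says that "ART adherence will be measured using hair samples assayed for tenofovir and emtricitabine", while the Quantitative Survey in section 9 also collects "self-reported adherence, adherence self-efficacy". The SAP does not say which adherence measure it summarises.

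No other section supplied gives an effect measure, an interval, a significance level or a power calculation.

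**The concern.** There are two separate faults in the one paragraph.

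First, the aim is estimation but no estimator follows. Examining differences and comparing trends describes an intention. It does not say whether the comparison is a risk difference, a ratio, or a difference in means or medians, and it attaches no measure of precision.

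Second, the reason given for having no significance results is wrong as statistics. Power is a property of a design against an assumed effect. When it is low, a test is unlikely to detect that effect and an interval is wide, but both can still be computed.

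At stake is how the preliminary-impact part of Aim 2 is read. Summaries set side by side invite a reader to treat an apparent trend as a finding, because nothing beside them shows how far it could be due to chance. The small sample is a reason to show that uncertainty.

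**Working it through.** The documents contain no power or precision figure to reproduce, so the figures below are illustrations.

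**Inputs**
- 40 women per arm: protocol section 10, Aim 2. This is a best case, because the SAP does not give the numbers analysed.
- 32 or 27 per arm at 6 months: two readings of the retention expectation in section 9 (Retention of Participants, Aim 2). 80% of those randomised gives 0.80 × 40 = 32; 80% of the 85% seen at 3 months gives 0.85 × 0.80 × 40 = 27.2.
- Rates near 50%: an assumption. Section 7 cites 49% viral suppression and 56% retention in care as background figures; they are not design inputs.
- Two-sided 95% intervals: an assumption.

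**1. Can anything be calculated at low power?** Take a case much smaller than planned, 7/10 against 5/10. The difference is 20 points, the Newcombe 95% interval is -20 to +53, and Fisher's exact p = 0.65. The result is uninformative, but it is calculable.

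**2. Is power in fact low?** Yes, plausibly. With two-sided alpha 0.05 assumed and control rates of 49% to 56%, power for a 20-point gain is 44–47% at 40 per arm, 37–39% at 32 and 32–34% at 27. The SAP is right about low power and wrong about its consequence.

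**3. Precision for a binary outcome.** Half-width = 1.96 × √(2p(1−p)/n), with p = 0.50:
- n = 40: 1.96 × √(0.50/40) = 0.219
- n = 32: 1.96 × √(0.50/32) = 0.245
- n = 27: 1.96 × √(0.50/27) = 0.267

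Worked case, 28/40 against 20/40. The difference is 0.700 − 0.500 = 0.200. The Wilson limits are 0.546 to 0.819 and 0.352 to 0.648. Newcombe:
- lower = 0.200 − √((0.700 − 0.546)² + (0.648 − 0.500)²) = −0.014
- upper = 0.200 + √((0.819 − 0.700)² + (0.500 − 0.352)²) = 0.390

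So a 20-point difference is compatible with anything from about -1 to +39 points.

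**4. What do medians and quartiles reveal for a continuous outcome?** I constructed samples of 32 per arm with values at quantiles (i − 0.5)/32, the same shape in both arms, and each scaled to an IQR of 1. Median and quartiles are therefore identical across shapes. The half-width for a mean difference is t(0.975, 62) × SD × √(2/32), which is 1.999 × SD × 0.25:

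| Shape | SD (IQR units) | Half-width (IQR units) |
|---|---|---|
| Uniform | 0.605 | 0.30 |
| Normal | 0.765 | 0.38 |
| t, 3 df | 0.984 | 0.49 |

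The planned summaries, with n, place the half-width somewhere in this range for these shapes but do not fix it.

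**The case against.** The best defence is that this is a pilot. It discloses its low power, claims no significance, and would be criticised if it tested efficacy. The closing clause can be read as loose wording for not claiming significance, and correcting it changes no analysis. All of that stands, and it is why p-values are not asked for. It does not answer the first fault: the paragraph sets itself an estimation aim and specifies no estimate.

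A reader might infer two stronger things that the documents do not support. One is that precision for the binary outcomes is lost unless denominators are added. The SAP plans frequencies together with percentages, and a count with its percentage fixes the denominator (28 at 70% means 40). A reader could compute the risk difference and its interval; the plan simply does not present them. The other is that nothing can be recovered for continuous outcomes. With n and the IQR an approximate interval for a mean difference is available; what is missing is an exact one. Among the three primary outcomes this clearly matters only for ART adherence, and only if hair drug levels are the measure.

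The illustration also has limits. The rates are assumed and the achieved n is unknown; the SAP's reference to small numbers may mean fewer than 27 per arm, in which case intervals would be wider still. Nothing in the documents says that the effect estimate will set the size of the next trial.

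**Conclusion.** The point holds in this limited form. The Intervention Impact paragraph states an aim to estimate an effect, names no between-arm measure and no interval, and gives an incorrect reason for the absence of significance results. Neither textual fault depends on the illustrative numbers.

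The size of the unstated uncertainty does depend on assumptions: rates near 50% and 27 to 40 analysed per arm give risk-difference half-widths of roughly 22 to 27 points. That is large enough for a 20-point trend to be compatible with no difference, as the worked case at 40 per arm shows.

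This should be fixed, but it does not invalidate the trial. The feasibility and acceptability analyses do not rely on this paragraph, and omitting hypothesis tests remains a sound choice.

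**What to change.** 1. Replace the closing clause with wording such as: *hypothesis tests were not planned because power was low*.
2. For each primary outcome in protocol section 6 (retention in care, ART adherence, viral suppression), at each follow-up time with data, report the between-arm difference by assigned arm, its 95% confidence interval and the number analysed in each arm. The condition on data matters for the chart outcomes, which are abstracted later: "During the passive follow-up period (7-12 months post-baseline").
3. Use a Newcombe risk difference for binary outcomes. For continuous outcomes fix one measure for all, in keeping with the planned medians: either the difference in medians with a bootstrap interval or the Hodges-Lehmann shift with its interval. Choose one and state it, because the two coincide only if the arms differ by a simple shift.
4. Say whether the mental health outcomes that the SAP lists under impact, which are not among the primary outcomes in section 6, are treated the same way as secondary outcomes.
5. Label the estimates exploratory, with no efficacy claim. The SAP is written in the past tense, so declare them post hoc if results had already been seen.

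The cost is a few sentences and a little more analysis of data already being summarised. The intervals will be visibly wide, which is the information now missing.
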